2.4.6 V wave recordings, contractile properties and octet contractions (aim #3)

Before and after long-term training, V waves will be recorded during 5 MVCs, with 1

min of rest between trials, via supramaximal electrical stimulation (150% of the current needed to evoke maximal M wave; 1-ms single square pulse) delivered to the tibial nerve when torque exceeds 90% MVC (52). Contractile muscular properties will be measured from muscle twitches evoked by three single pulses (1-ms square pulse) at 120% of the current needed to evoke maximal M-wave, delivered every 12s (74). Evoked octet contractions (8 pulses at 300Hz), which has been found to elicit the maximum capacity of rate of torque development, will be applied through three supramaximal pulses (at 120% of the current needed to evoke maximal M-wave), delivered every 12s (74).

2.4.7 H-recruitment curves and V-wave recordings with metaboreflex activation (aim #1, #2 and #3)

During the blood-flow occlusion trials, to ensure metabolite accumulation participants will previously perform a plantar-flexion contraction during 3 minutes at 40% MVC (aim #1). 25% MVC will be used in aim #2 and #3, in order to avoid any potential hypoalgesic effect to interfere with the analgesic effect of exercise or training protocols. There is evidence that 25% MVC isometric contraction for 5 min doesn't produce elevations in pain threshold (29) at the same time it is a contraction with sufficient intensity to produce nociceptive afferents activation (64). Then, using a rapid inflator system (Hokanson E20 AG101, Bellevue, WA), an adult-size cuff 12 x 124 cm (Hokanson, SC12L, Bellevue, USA) (placed on the upper portion of the thigh) will be inflated to a pressure of 300 mmHg to ensure complete blood-flow occlusion (75). This procedure will preserve the activation of group III/IV afferent fibers for subsequent measurement of H-reflex and V-wave excitability. To construct the H-recruitment curves, the upper current intensity (compatible with maximal M-wave) will be divided

into 22 segments equally separated on a logarithmic scale, with 4 stimuli/intensity, to limit the time under ischemia (~4 min), randomly applied to construct the recruitment curves, delivered at 3s intervals. After 2 min rest, the isometric plantar flexion contraction will be repeated with subsequent thigh circulatory occlusion. V waves will be ~~delivered~~ during 5 MVCs with 15 s of rest between trials (63) to limit the time under ischemia (~2 min), via supramaximal electrical stimulation (150% of the current needed to evoke maximal M wave; 1-ms single square pulse) delivered to the tibial nerve when torque exceeds 90% MVC. In control condition of aim #1 this H-reflex and V-wave collecting procedure will also be used but without sustained isometric contraction followed by blood flow occlusion. In aim #2 it will be assessed 15-30 min post-exercise or rest.

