isometric contraction followed by blood-flow occlusion) Vs. a control condition (no isometric contraction nor blood flow occlusion), on H-reflex recruitment curve and V wave excitability (aim #1). Since the activation of group III/IV afferents can inhibit the corticospinal pathway (61) we hypothesize that the normalized maximal amplitude and the slope of the ascending limb of the H-recruitment curve will decrease with metaboreflex activation. Additionally, we intend to examine the acute impact of different exercise modalities (resistance, supramaximal and endurance) on nociception sensibility (by the application of a cold tolerance test and by determining pressure pain threshold) (aim #2). This will allow us to investigate the role of different acute exercise paradigms on possible metaboreflex desensitization in its relationship with altered neuromuscular responses at post-exercise time point (attenuated inhibition of H-reflex and V-wave amplitude during metaboreflex activation). Also, once past research has shown that muscle metaboreflex activation reduces the sensitivity of the baroreflex (68), we will measure arterial pressure (AP) and heart rate variability (HRV) during cold pain tolerance testing. Despite all exercise modalities could enhance reducing pain sensibility after exercise, we hypothesize that resistance and supramaximal exercise stimuli will enhance nociceptive tolerance via metaboreflex desensitization compared to that seen with endurance exercise (attenuated increase of AP and sympathetic component of HRV during cold pressor test). Finally, we intend to explore the impact of long-term resistance, supramaximal and endurance training on nociceptive sensibility, using the same tests of aim #2 (aim #3). We hypothesize that chronic EIH will be of greater magnitude after supramaximal and resistance exercise training vs. endurance training. In addition, we hypothesize that decreased nociception will be related with attenuated inhibition of H-reflex and V-wave amplitude and attenuated increase of AP and sympathetic component of HRV during metaboreflex activation after training and this will result in increased exercise performance via heightened H-reflex and V-wave excitability.

2. Research Plan and Methods

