2.4.5 Standard H-recruitment curves (aim#3)

Before and after long-term training, standard methods will be used for M-wave and H-reflex recordings (52). These measurements will be taken while each participant maintains a submaximal low intensity contraction of the plantar flexors (10% MVC) with visual feedback from the dynamometer software being provided. The upper current intensity will be determined, firstly, by progressively increasing the current intensity by 5 mA from 0 until there is no further increase in peak torque or in peak-to-peak M-wave amplitudes. At each intensity level, three stimuli will be delivered at 3-seconds intervals. To construct the H-recruitment curves, the upper current intensity (compatible with maximal M-wave) will be divided into 22 segments equally separated on a logarithmic scale, with 16 stimuli/intensity randomly applied to construct the recruitment curves, delivered at 3s intervals.

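### Stimuli under occlusion are only put in random order; four complete randomised passes cost nothing and give a small precision gain if the reflex drifts

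*Combined protocol and SAP*

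**What the plan says.** Section 2.4.7 divides the current range into 22 log-spaced intensities, "with 4 stimuli/intensity, to limit the time under ischemia (~4 min), randomly applied to construct the recruitment curves, delivered at 3s intervals". It mentions no blocking, complete passes or other restriction on the order. The Aim #1 comparison run follows the same scheme: "this H-reflex and V-wave collecting procedure will also be used but without sustained isometric contraction followed by blood flow occlusion".

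Section 1.3 states the Aim #1 hypothesis: "the normalized maximal amplitude and the slope of the ascending limb of the H-recruitment curve will decrease with metaboreflex activation". Section 2.4.12 fits a curve to the ascending limb and extracts its parameters. Section 2.4.13 compares these by ANOVA. Neither section has a term for time within the run.

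Planned numbers are 16 participants in Aim #1 (2.1.1), 8 per modality in Aim #2 (2.2.1) and at least 8 per group in Aim #3 (2.3.1).

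**The concern.** Each occluded run follows a 3-minute contraction and continues for over four minutes without blood flow, so reflex amplitude may change while the curve is being collected. With only four stimuli per intensity, an unrestricted shuffle will by chance place some intensities mostly early and others mostly late. Any drift then shifts their means relative to each other, which disturbs the fitted slope and the maximum. Those are the two quantities named in the Aim #1 hypothesis, and they are compared within person in small samples. Because the analysis does not model time in the run, stimulus order is the only protection against drift. A more balanced order is available within the same 88 stimuli.

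**Working it through.** **Run length.** 22 × 4 = 88 stimuli; 88 × 3 s = 264 s = 4.4 min, consistent with the plan's figure of about 4 minutes.

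**Chance imbalance in time (no assumption beyond the order).**

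- *Shuffle.* The four times of one intensity are a sample without replacement from the 88 slots 0, 3, …, 261 s. The slot variance is 9 × (88² − 1)/12 = 5807.25 s². The SD of the mean is √(5807.25/4 × 84/87) = 37.4 s, or 37.4/264 = 14.2% of the run.
- *Four passes.* Each pass contributes one of 22 slots at random. The slot variance is 9 × (22² − 1)/12 = 362.25 s². The SD of the mean is √(362.25/4) = 9.5 s, or 3.6% of the run.

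**Approximate effect on one intensity's mean amplitude.** Assume a linear 20% drift over the run. The imbalance contributes 20% × 14.2% = 2.8% under the shuffle and 20% × 3.6% = 0.7% under passes. Stimulus noise in a mean of four is half the single-stimulus noise.

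- 10% noise: √(5² + 2.84²) = 5.75% vs √(5² + 0.72²) = 5.05%, a reduction of about 12%.
- 20% noise: √(10² + 2.84²) = 10.40% vs √(10² + 0.72²) = 10.03%, a reduction of about 4%.

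**Effect on the fitted curve (simulation).** A sigmoid was fitted to the level means. The assumptions were an ascending limb covering 10 of the 22 levels, linear drift and multiplicative noise, with 5000 runs per cell (3000 at 20% noise).

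| Assumed drift | Assumed noise | Slope CV, shuffle vs passes | Hmax CV, shuffle vs passes |
|---|---|---|---|
| 10% | 10% | 6.2% vs 5.9% | 4.2% vs 4.0% |
| 20% | 10% | 6.9% vs 6.0% | 4.8% vs 4.1% |
| 20% | 20% | 12.3% vs 11.9% | – |

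Mean slope differs between the two orders by about 1% or less, so the effect is noise and not bias. Other assumed curve shapes at 20% drift and 10% noise gave slope CVs of 6.3% vs 5.4%, 6.8% vs 5.8% and 7.7% vs 6.4%. A fast early drift of 20% in total gave 7.0% vs 6.1%. The gap at 20% noise is near simulation error: each CV has a standard error of about 12.3/√6000 = 0.16, so the difference of 0.4 has one of about 0.16 × √2 = 0.22.

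**Effect at group level, slope, 20% drift.** Let s be the SD of all other variation in the within-person difference (assumed 10–30%), a the shuffle CV, b the passes CV and c₀ the CV of a curve without drift. The ratio of variances is the equivalent gain in participants. Aim #1 has drift in the occluded curve only: (s² + c₀² + a²)/(s² + c₀² + b²). Aims #2 and #3 compare two occluded curves: (s² + 2a²)/(s² + 2b²).

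*10% noise (a = 6.9, b = 6.0, c₀ = 5.9).*

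- Aim #1, s = 10: 182.4/170.8 = 1.068; s = 30: 982.4/970.8 = 1.012. Sixteen participants are worth 16.2–17.1.
- Aims #2 and #3, s = 10: 195.2/172.0 = 1.13; s = 30: 995.2/972.0 = 1.024. Eight are worth 8.2–9.1.

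*20% noise (a = 12.3, b = 11.9, c₀ = 11.8, taken as twice 5.9).*

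- Aim #1, s = 10: 390.5/380.9 = 1.025; s = 30: 1190.5/1180.9 = 1.008. Sixteen are worth 16.1–16.4.
- Aims #2 and #3, s = 10: 402.6/383.2 = 1.05; s = 30: 1202.6/1183.2 = 1.016. Eight are worth 8.1–8.4.

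**The case against.** The strongest reply is that nothing is wrong. Random order already removes any systematic link between intensity and ischaemia time, and the wording may already mean randomised passes. The benefit depends on a drift that the documents do not quantify. The protocol aims for a held state: occlusion is meant to keep the afferents active (2.4.7), and arterial pressure is monitored to confirm it (2.4.10). Even if drift occurs, the gain is diluted by between-person variation and by stimulus noise.

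Most of this stands. It makes the point a conditional refinement. It does not remove it, because sustained afferent activation does not show that H-reflex amplitude is flat, and passes are the more balanced order at no cost.

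Three stronger readings are tempting, and the documents do not support them.

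- *That the random order biases the curves.* It does not; it can only add noise.
- *That cutting to four stimuli made the occluded curves worse balanced than the Aim #3 resting curves of 2.4.5, which are built* "with 16 stimuli/intensity randomly applied to construct the recruitment curves, delivered at 3s intervals". As a share of run length the resting imbalance is smaller (7.1% vs 14.2%). In seconds it is larger: √(9 × (352² − 1)/12/16 × 336/351) = 74.6 s vs 37.4 s. Which comparison matters depends on how drift accrues, and no contrast between the two kinds of curve is planned. The cut was made deliberately to limit ischaemia.
- *That the gain is large.* That requires drift well above 20%, for which the text gives no basis.

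**Conclusion.** The order in 2.4.7 is valid but, read as an unrestricted shuffle, is not the best free choice. The difference in time balance (37.4 s vs 9.5 s) is exact under that reading. What it is worth rests on assumed drift, stimulus noise and other variation. The gain is nil without drift and negligible at 10%. At 20% drift it is modest for a single curve if stimulus noise is about 10%, and close to undetectable if noise is about 20%. At group level it runs from nothing to a few per cent of participants in most of the settings examined. The upper ends, about 7% in Aim #1 and 13% in Aims #2 and #3, need both the lower noise and the smallest assumed other variation. This is an optional improvement, held with medium confidence.

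**What to change.** In 2.4.7, replace the instruction that the stimuli are applied randomly with: *delivered as four consecutive complete passes of all 22 intensities, each pass in a fresh random order*. Use the same scheme in the Aim #1 control condition, so that the two curves being compared are collected alike. If the investigators already work this way, the edit simply records it.

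The cost is one phrase and a new stimulus list. The 88 stimuli, the 264 s under occlusion, the staffing and the analysis stay as they are.

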2.4.7.1 Ischemia pain ratings (aim #1, #2 and #3)

The participants will be asked to rate the intensity of ischemia pain sensation using a 11-point (0–10) numerical scale (76), every 60s. The left end of the scale (=0) will be anchored with no pain, the middle of the scale will be anchored with moderate pain (=5) and the right end of the scale will be anchored with worst pain possible (=10).

2.4.8 Pressure pain threshold (aim #2 and #3)

Pressure pain threshold (PPT) will be assessed on the right rectus femoris (exercising muscle) and biceps brachii (non-exercising muscle). We will use a handheld algometer to perpendicularly deliver pressures to the participants' skin, and the pressure force will be increased at a rate of approximately $1 \text{ kg}\cdot\text{s}^{-1}$. The pressure will be stopped when they feel the pressure became painful. This procedure will be repeated three times for each test site. To minimize the impacts of repeated stimuli on the experimental outcomes, a recovery period of 20–30 s will be set between each measurement. The pain

pressure threshold will be recorded as the average of these three measures (34). In aim #2 it will be assessed 0-15 min post-exercise or rest.

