However, Ellingson et al. 2014 (36) showed that CPM is only a minor contributor to EIH due to differences in temporal and spatial manifestations. In fact, a significant CPM effect was observed only during evoked pain procedures (i.e. pressure), whereas EIH occurred following exercise. Also, during CPM a significantly larger effect on pressure thresholds was found at the remote sites compared to local sites, whereas EIH was significantly larger in the exercising body part compared to remote sites (13). Therefore, local and segmental mechanisms appear to play important roles for EIH.

Thus, the influence of exercise on reducing peripheral nociceptive sensitivity has also been explored as a mechanism of EIH (18). Preliminary data has provided indirect evidence that the hypoalgesic effect induced by exercise could be possible related to the modulation of the signal transmission via A-delta and C fibers. Using electroencephalographic evoked potentials, Jones et al. (2016) (11) verify that somatosensory-evoked potentials (SEPs) to noxious electrical stimuli delivered to the index finger were unchanged after elbow flexion isometric exercise at 40% MVC for 3 min, whereas laser-evoked potentials (LEPs) to noxious heat delivered to hand dorsum decreased after exercise. This result suggests that the peripheral nociceptor might be involved in EIH in humans, because laser heat stimuli activate peripheral afferents and electrical stimuli bypass the receptors by activating the axons of the nociceptive afferents (11). This was further corroborated by Jones et al. (2017) (37) where by blocking blood flow to an unexercised limb during cycling exercise, resulting in unchanged pressure pain threshold afterwards, provided evidence that factors that are released into the blood during exercise (opioids, cannabinoids, catecholamines), which interact with specific receptors, are able to inhibit the nociceptive signal and therefore modify input before reaching the central nervous system. Nevertheless, the effect of acute exercise on LEPs amplitude attenuation observed by Jones et al., (2016) (11) was not statistical different from the passive rest control condition. The approximately 230ms onset latency of LEP was only compatible with conductive velocity of fast myelinated A delta fibers. The augmented pressure pain threshold verified after exercise resulted from an assessment obtained over a period of

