2.2.2 Study design

In a randomized and crossover trial, on 2 different days, participants will be tested before and after performing acute bouts of different exercise modalities or

passive rest. Participants will be tested for: (1) pressure pain threshold, (2) cold pain tolerance with concomitant measures of AP and HRV, (3) the influence of metaboreflex activation (maintained submaximal isometric contraction followed by blood flow occlusion) on H-reflex and V-wave excitability. For those enrolled in endurance and resistance exercise modalities, participants will visit the laboratory on a previous day for $VO_{2\text{max}}$ and maximal repetition assessments for rigorous exercise prescription on experimental day. The experimental design is illustrated in figure 2.

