2.4.2 MVC (aim #1, #2 and #3)

All neuromuscular assessments will be made on the participants' dominant lower limb (plantar-flexors), using a Biodex System 3 Pro isokinetic dynamometer (Biodex Medical System 3). All testing sessions will be conducted between 07:00 and 11:00 hours, to avoid daily variations in muscle strength related to human circadian rhythms. Measurements will be taken in the seated position, with the participants maintaining their hips and knee flexed at 120° and ankle at 110° of plantar flexion (70). The flexed position at the knee joint will be used to reduce the mechanical contribution of the gastrocnemii to the plantar-flexor torque. Participants will be asked not to alter their posture and to focus on the task. MVC and rate of torque development (RTD) will be determined for plantar flexor muscles, based on three isometric contractions, lasting 5 s each. A 60 s interval of rest will be respected between trials. Participants will be instructed to exert their maximum force as fast and hard as possible with verbal encouragement and visual feedback from the dynamometer software being provided. The highest peak torque value will be defined as the participants MVC value (72, 73).

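### Aim #2: in right-dominant men the thigh used for pressure pain threshold is, by inference, also cuffed between the pre and post readings, and the planned ANOVA cannot separate cuff from exercise

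*Combined protocol and SAP*

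**What the plan says.** - **Pain site (2.4.8).** "Pressure pain threshold (PPT) will be assessed on the right rectus femoris (exercising muscle) and biceps brachii (non-exercising muscle". The thigh side is fixed as right for everyone. In Aim #2 the post reading falls in the first 15 minutes after exercise or rest.
- **Test limb (2.4.2).** "All neuromuscular assessments will be made on the participants' dominant lower limb (plantar-flexors". The side therefore varies between men.
- **Cuff (2.4.7).** The cuff is "placed on the upper portion of the thigh) will be inflated to a pressure of 300 mmHg to ensure complete blood-flow occlusion". The side is not written. It is inflated once for the H-reflex curve and again for the V waves. In Aim #2 the post-intervention cuffing comes 15 to 30 minutes after exercise or rest, so after the post threshold reading.
- **Design (2.2.2).** In a crossover over two days, "participants will be tested before and after performing acute bouts of different exercise modalities or" passive rest. The tests are listed as pressure threshold first, cold tolerance second, metaboreflex test third.
- **Analysis (2.4.13).** For Aim #2 the factors are time (before and after acute exercise) and condition (the three modalities). Passive rest is not a level of either factor, and measurement site is not a factor.
- **Safeguard (2.4.7).** The preparatory contraction is lowered to 25% MVC in Aims #2 and #3 so that it does not itself produce hypoalgesia. Nothing comparable is said about the cuff.

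**The concern.** Read together, these sections place a local exposure between the two readings whose difference is meant to show the exercise effect. In a right-dominant man, the thigh tested after exercise was compressed and made ischaemic during the pre-exercise battery. In a left-dominant man the right thigh was not, and the biceps never is.

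If a released cuff leaves the muscle more tender or less sensitive for a while, that change is added to or subtracted from the exercise effect at the thigh. It could create an apparent hypoalgesia or hide a real one. The authors saw the general problem, because they lowered the contraction intensity to keep the test from interfering with the pain outcomes, but that step does not cover the cuff.

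**Working it through.** **1. Occlusion time per battery (2.4.7).**
- H-reflex curve: 22 intensities × 4 stimuli × 3 s = 264 s = 4.4 min. The protocol gives about 4 min, so its figure is reproduced.
- V waves: 5 contractions with 15 s rests. Taking 5 s per contraction (the MVC duration in 2.4.2, assumed to apply here), 5 × 5 + 4 × 15 = 85 s = 1.4 min. The protocol gives about 2 min.
- Total: 4.4 + 1.4 = 5.8 min to 4.4 + 2 = 6.4 min, or about 6 min.

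**2. Sequence in a right-dominant man, if the listed order is followed.** Pre threshold (right thigh) → cold test → cuff twice (right thigh, inferred) → exercise or rest → post threshold (right thigh) → cold test → cuff twice. One battery's occlusion therefore lies between the two readings.

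**3. Minimum gap from last cuff release to post reading (2.2.3).**
- Supramaximal: 0.5 + 4 + 0.5 = 5 min.
- Endurance: 30 min.
- Resistance and passive rest: duration not stated.

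Any interval between the pre battery and the bout would lengthen these gaps; none is given.

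**4. Effect on the planned tests.** The documents give neither the size of a cuff after-effect nor the share of right-dominant men, so both are assumptions. Let c be the shift, in SDs of the threshold change score, and q the right-dominant share. The simulation used 40,000 runs, 24 men in three groups of 8, no true exercise effect and alpha 0.05.

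Rough check at c = 0.5, q = 0.9: the mean shift is 0.5 × 0.9 = 0.45 SD, and 0.45 × √24 = 2.2 standard errors, close to the critical value. Rejection should therefore occur in roughly half of runs; the simulation gives 55%.

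| Assumed c | Time effect as planned (q = 0.8 to 1.0) | Modality interaction, equal cuff effect | Exercise minus rest, matched interval |
|---|---|---|---|
| 0 | about 5% | about 5% | about 5% |
| 0.2 | 12–15% | about 5% | about 5% |
| 0.5 | 45–65% | about 5% | about 5% |
| 0.8 | 81–96% | about 5% | about 5% |

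The last column covers both the time and the interaction test.

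**5. If the after-effect decays with bout length.** With assumed weights of 1 (supramaximal), 0.6 (resistance) and 0.2 (endurance), and q = 0.9, the interaction test rejects in about 6%, 9% and 14% of runs for c = 0.2, 0.5 and 0.8. Subtracting a rest session whose interval is not matched (weight 1 for everyone) leaves 5%, 7% and 10% for the interaction, and 6%, 9% and 16% for the time effect. Matching the interval brings both back to about 5%.

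**The case against.** The strongest reply is the passive-rest session. Each man repeats the battery on a rest day, with the same cuffing of the same thigh, and leg dominance is constant within a man. Exercise change minus rest change would therefore remove the cuff effect if the intervals match. This stands as a property of the design, but 2.4.13 does not use it: rest is absent from the model, and without a stated rest length cancellation is not assured.

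Other points also stand:
- A reader might infer that cuff after-effects will be reported as local hypoalgesia. The documents give no direction; soreness would lower the threshold and hide hypoalgesia.
- A reader might take section 1.1 as proof of carry-over. It describes an effect seen "by blocking blood flow to an unexercised limb during cycling exercise, resulting in unchanged pressure pain threshold afterwards". That was occlusion during exercise; here the cuff is released before exercise starts. Nothing in the documents shows that a released cuff alters a later threshold.
- A reader might infer a biased thigh-versus-biceps test. The two sites do differ in cuff exposure, but 2.4.13 plans no test of site.
- The cuff side is inferred, the pre-battery order is only a numbered list (Figure 2 is not shown), and the distance from algometer point to cuff is not given. If the cuff came before the pre threshold, the pre reading would be the more recently exposed one; the imbalance would remain in another form.

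**Conclusion.** The concern holds as a confounding of cuff and exercise in the Aim #2 pre-post change at the thigh. It applies to right-dominant men and rests on two inferences: the cuff is on the dominant leg, and the pre battery follows the listed order. The exposure is about 6 minutes of 300 mmHg occlusion.

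Under the ANOVA as written, any resulting shift goes into the time effect. The modality interaction is disturbed only if the after-effect fades over gaps that range from about 5 to 30 minutes. Confidence is high on the overlap and low on the size of its effect: the false-positive rates above show sensitivity to assumed shifts and do not predict the actual bias. The carry-over does not arise in Aim #3, where the pre and post readings are separated by the six-week training period. The change is worth making because it removes the local exposure whatever its size or direction.

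**What to change.** 1. **Section 2.4.8.** Measure thigh threshold on the rectus femoris of the leg not used for cuff occlusion and nerve stimulation. Leg press, calf raise, cycling and running all load both legs, so that thigh is still an exercising muscle. Use the same side in Aim #3, for consistency only.
2. **Section 2.4.13.** For Aim #2, add session (exercise or rest) by time, and its interaction with modality. This also handles carry-over from the pre battery that is not confined to the cuffed thigh, which moving the site would not.
3. **Section 2.2.2.** State the rest duration, matched to the man's exercise bout, and the order of the pre battery. State the cuff side in 2.4.7, and record leg dominance.

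**Cost.** The site change is one sentence, with no added time or equipment. Its small downside is that thigh threshold is no longer on the limb where the H-reflex and V wave are recorded, although those come from the soleus and the threshold from the rectus femoris. The model change uses data already planned but is noisier. If the changes on the two days are uncorrelated (an assumption), the SD of their difference is √2 = 1.41 times that of one change. The effect detectable with 80% power in a paired test of 24 men then rises from 0.60 to 0.60 × 1.41 = 0.85 SD of a single-session change. Positive correlation between days would reduce that loss.
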